5.7.2 Food and Fluid Intake Restrictions

Consumption of foods and beverages containing the substances listed below will be prohibited as indicated. Exceptions may be permitted upon the joint agreement of the Sponsor and the Investigator provided the safety of the subject and integrity of the study are not compromised.

- Caffeine/xanthines: Prohibited 4 hours prior to daily dosing

For Visits 2 and 4, subjects will be provided with a diary card and instructed to record times of meal consumption beginning three days prior to these visits and during these visits. The Investigator will record this information on the eCRF.

5.7.3 Lifestyle Restrictions

Consumption of tobacco products will be prohibited during the study. Subjects who have any history of regular tobacco product use more recently than 3 months prior to Screening will not be allowed in the study.

6 STUDY PROCEDURES AND ASSESSMENTS

6.1 Informed Consent

According to the ICH guideline for GCP (E6) and all institutional local, state, and federal laws, the Investigator will obtain and document an ICF for each subject screened for this study. All subjects will be informed in writing of the nature of the protocol and investigational therapy, its possible hazards, and their right to withdraw at any time, and will sign a form indicating their consent to participate prior to the initiation of study procedures. The subject's medical record should contain written documentation indicating that informed consent was obtained. The ICF must be reviewed and approved by the Investigator's designated IRB and by Viking Therapeutics, Inc. clinical staff. The ICF should include all the elements as outlined in Section 4.8.10 of the ICH guideline for GCP (E6).

6.2 Medical History

At Screening, a complete medical history and social history, including smoking, caffeine and alcohol use, will be collected by subject interview. Concomitant medications, recent blood donations, illnesses, and participation in other investigational drug studies will also be recorded.

6.3 Physical Examination

A physical examination including weight will be performed at Screening, Visit 2, Visit 4, Visit 5, and in case of early withdrawal. Height will be measured at Screening only.

6.4 Vital Signs

Vital signs will be recorded at every clinic visit. Vital signs including seated blood pressure (two blood pressure readings separated by 2 minutes), heart rate (measured after the first blood pressure reading), will be measured after the subject has been seated for at least 5 minutes. The recorded value will be the mean of two measurements. Vitals signs will be measured prior to any blood draw that occurs at the same time point.

6.5 Electrocardiography (ECG)

6.5.1 ECG Acquisition

An ECG will be performed at Screening, Randomization (at 2 hours post-dose), Visit 4, and Visit 5. The 12-lead ECG equipment will be set to 25mm/sec and 10mm/mV. The operator will enter selected subject demographic information prior to obtaining the ECG. The following subject information will be entered into the machine:

- Subject initials (example: XYZ or X-Z).
- Subject number.
- Subject date of birth (mm/dd/yyyy).
- Study day and time.

ECGs will be recorded with subjects in the recumbent position and resting. Subjects will have been in this resting position for 5 minutes prior to ECG recording and performed prior to any blood draw that occurs at the same time point.

In case of baseline tremor, measures will be taken to eliminate this as it may interfere significantly with the quality of the interpretation. Prior to electrode placement, the 10 anatomical sites will be prepared to allow for proper skin/electrode interface.

6.6 Mini Mental State Exam (MMSE)

The MMSE will be performed at Screening to evaluate cognitive function. A description and copy of the exam are provided in [Appendix 15.1](#).

6.7 Four-Meter Walk Test

The 4-meter walk test will be performed at Screening to evaluate the subject's ability to ambulate. The subject will be instructed to walk a continuous, straight four meters without turns. Use of a cane or walker is permitted. The subject must be walking with a gait speed of <0.8 m/s.

6.8 Physical Performance Assessments

All physical performance assessments will be done at the Randomization visit and at Visits 2, 3, 4, and 5 as shown in [Table 1](#). These assessments will also be done in case of early withdrawal.

6.8.1 Six-Minute Walk Test (6MWT) and BORG Scale

The 6MWT will be used to assess functional cardiovascular status. The BORG Scale will also be administered. This test may be performed as part of the physical examination. Instructions are provided in [Appendix 15.2](#).

6.8.2 Grip Strength

Grip strength is used to provide a generalized assessment of upper body strength. Instructions for use of the Dynamometer are provided in [Appendix 15.3](#).

6.8.3 Short Physical Performance Battery (SPPB)

The SPPB test is a group of assessments that examines walk speed, chair stand, and balance. Scores range from 0 to 12 and instructions are provided in [Appendix 15.4](#).

6.9 Patient Reported Outcomes

6.9.1 Short Form-36 (SF-36)

The SF-36 questionnaire will be conducted by subject interview at Randomization, Visit 4, Visit 5, and in case of early withdrawal as shown in [Table 1](#). A sample questionnaire is provided in [Appendix 15.5](#).

6.9.2 Physical and Instrumental Activities of Daily Living (PADLs/IADLs)

PADLs/IADLs will be conducted by subject interview at Screening, Randomization, Visits, 2, 3, 4, and 5 and in case of early withdrawal as shown in [Table 1](#). At Screening, only the pre-fracture PADLs/IADLs will be conducted by subject interview. At all other visits, only the post-fracture PADLs/IADLs will be conducted. The pre-fracture PADLs/IADLs questionnaire is provided in [Appendix 15.6](#); the post-fracture PADLs/IADLs questionnaire is provided in [Appendix 15.7](#).

6.10 DXA Scans

DXA scans will be performed at Randomization and at Visits 4 and 5, or in case of early withdrawal as shown in [Table 1](#). Instructions for DXA scans are provided in the study reference manual.

6.11 Clinical Laboratory Tests

All details regarding clinical laboratory sample collection, preparation, and shipment will be included in the laboratory manual provided by the central laboratory and the Viking pharmacokinetics manual provided by Viking Therapeutics, Inc.

In the event of abnormal clinical laboratory values, the Investigator will make a judgment whether or not the abnormality is clinically significant.

6.11.1 Laboratory Parameters

Clinical laboratory tests will include the following:

Serum Chemistry

- Sodium
- Potassium
- Chloride
- Alanine aminotransferase (ALT; SGPT)
- Aspartate aminotransferase (AST; SGOT)
- Gamma-glutamyl transferase (GGT)
- Total bilirubin (TBIL)
- Alkaline phosphatase (ALP)
- Albumin
- Total Protein (TP)
- Blood urea nitrogen (BUN)
- Creatinine
- Glucose
- Calcium
- Phosphate
- HbA1c (Screening only)

Hematology

- Hemoglobin
- Platelet count

- Red blood cell count
- White blood cell count with differential

Additional tests

- Vitamin D
- T3, T4, and TSH
- s-CTX and s-PINP

These tests will be performed according to the schedule of events ([Table 1](#)).

6.11.2 Urinalysis

Urinalysis parameters for clinical laboratory tests include the following:

• appearance• bilirubin• color• glucose• ketones• leukocyte esterase	
• occult blood• pH• protein• specific gravity• urobilinogen
---	---

6.11.2.1 Special Laboratory Tests for Hormone Levels, Hematology, Lipids, and Kidney/Pancreatic Function

Pituitary/Adrenal Hormone Blood Tests

- FSH
- LH
- SHBG
- FT
- TT
- Estradiol
- Adrenocorticotrophic hormone (ACTH)
- Cortisol
- Aldosterone

Male Hormone

- Prostate-specific antigen (PSA)

Fasting Lipid Profile

- Total Cholesterol
- LDL
- HDL
- Triglycerides
- Cholesterol/HDL ratio (calculated)
- Non-HDL Cholesterol (calculated)

Pancreatic Endocrine Markers

- Fasting insulin

Fasting glucagon

Coagulation

- Prothrombin time (PT)
- Partial thromboplastin time (PTT)

6.11.3 These tests will be performed according to the schedule of events ([Table 1](#)). Sample Collection, Storage and Shipping

Blood samples for hematology and serum chemistry will be collected according to the laboratory manual provided by the central laboratory and according to the schedule of events ([Table 1](#)).

6.12 Plasma Concentration Sample Collection

Blood samples to determine plasma study drug concentration will be collected at Visits 2, 3, 4 and 5 as shown in [Table 1](#).

Pre-dose samples will be collected on the appropriate days at 0 to 20 min pre-dose (Visits 2, 3, and 4). A single post-dose sample will be collected thereafter at 2 hours (\pm 10 min) post-dose (Visits 2, 3, and 4), plus one additional sample at Visit 5.

At each collection, 5 mL of blood will be collected into a Vacutainer tube containing lithium heparin (green top) and immediately placed in an ice bath. Within 30 minutes of collection, the plasma fraction will be separated by centrifugation at 2,500 rpm (1,000 x g) for 15 minutes at 4°C. The plasma fraction will be separated into equal aliquots and transferred into 2 labeled 5 mL polypropylene tubes and frozen at approximately -20°C or -70°C.

Blood volume collected for these samples will be approximately 20 mL total per subject.

Plasma concentration samples should be shipped on dry ice via overnight delivery to MicroConstants for analysis. Samples will ship only on a Monday, Tuesday or Wednesday to minimize the possibility of the samples being in transit over a weekend. Duplicate plasma concentration samples will ship after MicroConstants confirms receipt of the initial samples.

6.13 Concomitant Medication Assessments

All medications or treatments study subjects are taking or have taken during the 30 days prior to treatment will be recorded in the subject's record and the eCRF. Any bisphosphonate medication taken during the 5 years prior to treatment will also be recorded in the subject's record and the eCRF. All treatments administered to subjects following the first dose of the study drug will be recorded in the subject's record and the eCRF. Medications administered should be recorded according to the generic name when possible. Concomitant medications should be limited to those that are medically necessary. Any concomitant medication used should have an indication recorded and this indication must be represented as either an adverse event, for the management of a pre-existing condition, or for prophylaxis.

Dosage increases for any concomitant medication should be noted and the reason for the dosage increase recorded as an adverse event (assumes worsening condition). The side effects of concomitant medications will be recorded as adverse experiences.

Any subject whose condition becomes disqualifying during the course of the study may be treated for that condition. If condition is suspected during screening the subject should not be enrolled. Treatment of the condition should be instituted according to the Investigator's/attending physician's judgment.

Drugs that have no treatment intent but rather are part of supportive routine care such as local anesthetics, intravenous solutions to maintain fluid balance and keep access open, medications used for prophylaxis, and narcotics for postsurgical pain must also be recorded in the eCRF.

7 STUDY ACTIVITIES

7.1 Screening Visit (Day -7± 2)

At the initial Screening, potential subjects will be given a detailed presentation describing the nature, purpose, risks, and requirements of the study and will also receive detailed written information.

They will have adequate opportunity to ask the appropriate person of the clinical staff (i.e., Principal Investigator or designee) presenting the study about any aspect of the study. Once the subject is satisfied that he/she is willing to participate in the study, he/she will be asked to sign the study ICF. The ICF will include all the elements as outlined in Section 4.8.10 of the ICH guidelines for GCP (E6). The clinical personnel obtaining written consent from the subject will also sign the form to confirm consent has been obtained.

Once signed, the Investigator will retain the original for the subject's study records and provide the subject with a signed copy. The Investigator will verify that informed consent has been obtained from each subject prior to admission into the study and prior to the subject undergoing any study-related procedures.

Within 3-11 weeks post-fracture, all screening activities subsequent to obtaining informed consent will be conducted and consist of the following:

- Satisfaction of inclusion/exclusion criteria ([Section 4](#))
- Completion of medical and social history including tobacco, alcohol, and caffeine use
- Concomitant medications assessment
- Collection of demographic data (sex, age, race/ethnicity)
- Mini Mental State Exam (MMSE)
- Physical examination, including height and weight
- 4-Meter Walk Test
- Vital signs (SBP, DBP, HR)
- ECG
- Clinical laboratory tests including hematology, chemistry (with HbA1c) and urinalysis ([Section 6.6](#))
- Prostate-specific Antigen (PSA) test, males only
- Pre-fracture PADLs/IADLs
- Schedule the Baseline DXA scan.

Subjects who fulfill all inclusion and exclusion criteria will be randomized within 9 days of

Screening.

7.2 Screening Failures

A screening failure is defined as a subject who has signed the ICF, does not meet all the entry criteria outlined in [Section 4](#) of this protocol and has not been randomized or received study treatment. The Investigator (or designee) will describe the reason for the screening failure in the EDC system.

7.3 Randomization/Baseline (Day 0)

Randomization will occur approximately one week after Screening. The following activities will be performed according to the schedule of events in [Table 1](#):

- Record concomitant medications
- Record adverse events
- Vital signs (SBP, DBP, HR)
- Hematology/Chemistry/Urinalysis
- Bone Turnover Markers
- Vitamin D
- Thyroid Markers Pituitary/Adrenal Hormone Blood Tests
- Pancreatic Endocrine Markers
- Fasting Lipid Profile
- Coagulation
- A light snack is permitted after bloodwork has been completed.
- DXA Scan
- ECG at 2 hours post-dose
- Grip Strength and SPPB (to be performed before the PADLs/IADLs and SF-36)
- Post-fracture PADLs/IADLs
- SF-36
- 6MWT and BORG Scale (to be performed after the PADLs/IADLs and SF-36)
- Study drug administration; dispense 4-week supply of study drug and provide dosing instructions
- Provide diary card to record treatment administration and meal and snack times for 3 days prior to Visit 2

7.4 Visit 1 Telephone Contact (Day 7 -5/+2)

At Visit 1, the following will take place:

- Record concomitant medications
- Record adverse events
- Review study treatment compliance

7.5 Visit 2 (Day 28 -5/+2)

At Visit 2, the following will take place:

- Record concomitant medications

- Physical examination, including weight
- Vital signs (SBP, DBP, HR)
- Plasma concentration sample collection (pre-dose and 2 hours \pm 10 min post-dose)
- Hematology/Chemistry/Urinalysis
- Bone Turnover Markers
- Pituitary/Adrenal Hormone Blood Tests
- Pancreatic Endocrine Markers
- Fasting Lipid Profile
- Coagulation
- A Light snack is permitted after bloodwork has been completed.
- Grip Strength and SPPB (to be performed before the PADLs/IADLs)
- Post-fracture PADLs/IADLs
- 6MWT and BORG Scale (to be performed after the PADLs/IADLs)
- Record adverse events
- Review diary card
- Review study treatment compliance; administer and dispense/re-dispense study treatment

7.6 Visit 3 (Day 56 -5/+2)

At Visit 3, the following will take place:

- Record concomitant medications
- Vital signs (SBP, DBP, HR)
- Plasma concentration sample collection (pre-dose and 2 hours \pm 10 min post-dose)
- GGT, ALT, AST, and total bilirubin
- Bone Turnover Markers
- Pancreatic Endocrine Markers
- Grip Strength and SPPB (to be performed before the PADLs/IADLs)
- Post-fracture PADLs/IADLs
- 6MWT and BORG Scale (to be performed after the PADLs/IADLs)
- Record adverse events
- Review study treatment compliance; dispense/re-dispense study treatment
- Provide diary card to record treatment administration and meal and snack times for 3 days prior to Visit 4
- Schedule the Visit 4 DXA scan.

7.7 Visit 4 (Day 84 -5/+2)

At Visit 4, the following will take place:

- Record concomitant medications
- Physical examination, including weight
- Vital signs (SBP, DBP, HR)
- Plasma concentration sample collection (pre-dose and 2 hours \pm 10 min post-dose)

- ECG at 2 hours post-dose
- Hematology/Chemistry/Urinalysis
- Thyroid Markers
- Vitamin D
- Bone Turnover Markers
- Pituitary/Adrenal Hormone Blood Tests
- Pancreatic Endocrine Markers
- Fasting Lipid Profile
- Coagulation
- PSA (males only)
- A light snack is permitted after bloodwork has been completed.
- DXA Scan
- Grip Strength and SPPB (to be performed before the PADLs/IADLs and SF-36)
- Post-fracture PADLs/IADLs
- SF-36
- 6MWT and BORG Scale(to be performed after the PADLs/IADLs and SF-36)
- Record adverse events
- Review diary card
- Review study treatment compliance and administer study treatment
- Schedule the Visit 5 DXA scan.

In case of early withdrawal, all Visit 4 events should be performed, excluding plasma drug concentration assessments and study drug dispensation.

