Approximately 8 weeks (no more than 60 days) after randomization, subjects will report to the clinic for Visit 3 and provide samples for plasma concentration, chemistry (GGT, ALT, AST, and total bilirubin), bone turnover markers and pancreatic endocrine markers. Vital signs will be measured. Subjects will provide data for Grip Strength, and SPPB. Post-fracture PADLs/IADLs will be conducted by subject interview. Following the interviews, they will perform the 6MWT and BORG Scale. Concomitant medications, adverse events, and compliance will be reviewed and the next bottle of study treatment (30 capsules) will be dispensed. Subjects will be informed that they may have more doses than they will need and must return any extra study treatment at Visit 4. They will receive a diary card to record their treatment administration and meal and snack times for 3 days prior to Visit 4. Subjects will be informed that they may have more doses than they will need and must return any extra study treatment at Visit 4. Visit 4 DXA scans should be scheduled at this time.

2.7 Visit 4

Approximately 12 weeks (no more than 90 days) after randomization, subjects will report to the clinic following a minimum 10-hour fast at approximately 8 am (Visit 4). A pre-dose blood sample will be drawn for the fasting lipid profile. A pre-dose plasma concentration blood sample will be drawn, the subject will be provided with one dose of their assigned treatment, and a post-dose plasma concentration blood sample will be drawn at 2 hours (± 10 min). Diary card data, concomitant medications, compliance, and adverse events will be reviewed. They will have a physical examination, including weight, and vital signs will be measured. They will provide safety assessment samples for hematology/chemistry/urinalysis and additional blood samples for bone turnover markers, serum calcium, vitamin D, thyroid markers, pituitary/adrenal hormones, PSA (males only), coagulation, and pancreatic endocrine markers. Following these blood tests, subjects will be allowed to have a light snack. Subjects will provide data for Grip Strength, and SPPB. Post-fracture PADLs/IADLs and SF-36 will be conducted by subject interview. Following the interviews, they will perform the 6MWT and BORG Scale. ECG and DXA scans will be performed. Visit 5 DXA scans should be scheduled at this time.

2.8 Visit 5

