2.9 Early Termination

In case of early termination, the events will be performed according to [Table 1](#) and will be identical to Visit 4, excluding plasma concentration sample collection.

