5.2 Treatment Quantity, Schedule and Form of Administration

Subjects will be provided with 1 bottle of VK5211 or placebo containing 30 capsules at Randomization. The clinical site will dispense one bottle at Randomization, Visit 2, and Visit 3. At each Visit, the previous bottle will be returned by the Subject and either re-dispensed to the subject or retained at the site until further notice from the Sponsor.

Subjects will be provided with a diary card at Randomization and Visit 3 and instructed to record times of dosing administration and meals and snacks beginning three days prior to Visits 2 and 4. The Investigator or designee will record this information on the eCRF.

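### Protocol 7.7 leaves the in-clinic dose and the ECG 2 hours after it in place at early withdrawal, contrary to Table 1

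*Protocol*

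**What the plan says.** The Visit 4 checklist in Protocol 7.7 has one item on study drug, "Review study treatment compliance and administer study treatment", and one on the electrocardiogram, "ECG at 2 hours post-dose". It has no dispensing item. The section closes with the rule for early withdrawal: "all Visit 4 events should be performed, excluding plasma drug concentration assessments and study drug dispensation".

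Section 2.9 (Early Termination) says in its first clause that the events follow Table 1. Its second clause says that they are "identical to Visit 4, excluding plasma concentration sample collection". The narrative for Visit 4 in Section 2.7 includes one dose of the assigned treatment, given in the clinic between the pre-dose and post-dose plasma samples.

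Table 1 settles both items. Footnote 11 gives compliance and administration for Visit 4, but compliance alone for Early Termination. Footnote 2 places the ECG 2 hours after the dose at Randomization and Visit 4 only, and the ECG mark in the Early Term column does not carry that footnote.

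**The concern.** The early-withdrawal sentence in 7.7 excludes a drug-related act that the Visit 4 list does not contain and leaves in the one that it does contain. A coordinator working through 7.7 as a checklist would keep the dose and time the ECG to it. The sentence does not refer to Table 1, so nothing at that point corrects the reading.

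What is at stake is the safety of the individual subject. Section 4.3 lists intolerable adverse effects among the reasons for discontinuation, and a subject leaving for that reason should not receive another dose at the exit visit.

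**Working it through.** The plan gives no figure to reproduce, and no power or error-rate formula applies. The check is to set the instructions side by side.

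| Item | Visit 4 list in 7.7 | Early withdrawal, 7.7 read literally | Second clause of 2.9 | Table 1, Early Term column |
|---|---|---|---|---|
| Plasma samples | listed | excluded | excluded | no mark |
| Dispensing | not listed | excluded | not mentioned | none (footnote 11) |
| In-clinic dose | listed | kept | kept, through 2.7 | none (footnote 11) |
| ECG | 2 hours post-dose | kept, 2 hours post-dose | kept; 2.7 gives no timing | marked, without footnote 2 |

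1. *Dose.* 7.7 keeps it and footnote 11 does not. Both are instructions to the site about the same visit, so they contradict each other.

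2. *ECG.* 7.7 carries over the post-dose timing. Footnote 2 limits that timing to two other visits. Table 1 requires the early-termination ECG but does not tie it to a dose, so the conflict is over timing and not over whether the ECG is done.

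3. *Could dispensation mean administration here?* The visit lists use two different words. Visit 2 has "Review study treatment compliance; administer and dispense/re-dispense study treatment", Visit 3 has "Review study treatment compliance; dispense/re-dispense study treatment", and Visit 4 has administration without dispensing. Footnote 11 makes the same split. Section 5.2 gives the dispensing exclusion a little possible work to do, since "At each Visit, the previous bottle will be returned by the Subject and either re-dispensed to the subject or retained at the site". On neither view does the word, as written, cover a dose given in the clinic.

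4. *Does removing the plasma samples remove the dose?* Only by inference. In 2.7 the dose sits between the two samples, so without them one reason for it goes. But 7.7 still lists the dose as a separate item, and its timed ECG is a second reason to give it.

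5. *Size.* One visit carries at most one dose. Allocation is 1:1:1:1 across 0.5 mg, 1.0 mg, 2.0 mg and placebo, so the dose would be VK5211 in 3 of 4 arms. The documents give no expected number of early-termination visits. SAP 2.14 plans to randomize 104 so that about 92 complete, which leaves 104 − 92 = 12 not completing. It does not say how many of those would attend an exit visit, so 12 is not a count of affected subjects.

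**The case against.** The strongest reply is that the documents already hold the right answer. Section 2.9 first sends the site to Table 1, and footnote 11 is explicit. Section 4.3 calls the exit assessments post-treatment evaluations, and Section 5.5 has unused drug handed back at the Early Termination Visit. A site would have to overlook all of this, and the reason for withdrawal, to give the dose. This stands as far as it goes: the intent can be recovered, and harm is unlikely. It does not rescue 7.7, whose sentence stands alone, and neither document says whether text or table takes precedence.

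Three stronger readings are tempting, and the documents do not support them.

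- *That 2.9 is as wrong as 7.7.* It is not. Its first clause points to the correct schedule. Its second clause is loosely worded and conflicts with the table just cited.
- *That the protocol uses administer and dispense so strictly that the lists show exactly when subjects are dosed.* Visit 3 shows otherwise. Section 6.12 and footnote 9 require samples before and 2 hours after a dose at Visit 3, so a dose must be taken, yet neither 7.6 nor footnote 11 lists administration there. The point therefore rests on the mismatch between 7.7 and Table 1, not on a strict vocabulary.
- *That the ambiguity contaminates the ECG summaries by mixing dosed and undosed recordings.* That mixing occurs under the intended schedule too. Table 1 has post-dose ECGs at Visit 4 and ECGs not tied to a dose at early termination, and SAP 2.16 places early-termination data up to Day 112 (84 + 28) in Month 3. Correcting 7.7 would not change this, and SAP 2.9.4 plans only descriptive summaries of ECGs.

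A reader might also picture a subject stopped for QTc prolongation being dosed again. Section 4.3 states that such subjects are discontinued from treatment, so a site has a direct instruction against it.

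**Conclusion.** Section 7.7 is wrong as written, and the second clause of 2.9 needs tightening. The finding is minor. The consequence is limited to a possible single unintended dose for a subject who is being withdrawn, and only at a site that follows 7.7 literally instead of Table 1. There is no effect on power, alpha, the primary endpoint or any planned test. The conclusion assumes that Table 1 expresses the intended schedule, which its separate entries for Visit 4 and Early Termination support.

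**What to change.** In 7.7, name study drug administration alongside dispensation in the early-withdrawal exclusion, next to the plasma concentration assessments, and state that the early-termination ECG is not timed to a dose. Add the same exclusion to 2.9 so that its second clause agrees with the table it cites. Leave Table 1 unchanged.

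The cost is a wording change in two sections, with no new procedure, no change to the schedule and no change to the analysis.
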